1.1.1. Inclusion Criteria for Enrollment

1. Willing and able to provide written informed consent prior to performing study procedures or have a legally authorized representative available to do so.
2. Age ≥ 18 years.
3. Evidence of SARS-CoV-2 infection by PCR test of nasopharyngeal swab or oropharyngeal swab/tracheal aspirate sample within 14 days of randomization.
4. Peripheral capillary oxygen saturation (SpO_2) $\leq 94\%$ on room air or requiring supplemental oxygen, non-invasive or invasive mechanical ventilation at screening.
5. Evidence of infiltrates on chest radiography.
6. Females of childbearing age and males must be willing to practice an effective contraceptive method or remain abstinent during the study period.

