1. To compare duration of need for supplemental oxygen and/or mechanical ventilation between recipients of the anti-SARS-CoV-2 plasma and control plasma.
2. To compare duration of hospitalization between recipients of the anti-SARS-CoV-2 plasma and control plasma.

3. To compare in-hospital and 28-day mortality between recipients of the anti-SARS-CoV-2 plasma and control plasma.

Ancillary Endpoints:

1. To compare the proportion and duration of SARS-CoV-2 PCR positivity (RT PCR) between recipients of the anti-SARS-CoV-2 plasma and control plasma at days 0, 7, and 14.
2. To compare the levels of SARS-CoV-2 RNA between recipients of the anti-SARS-CoV-2 plasma and control plasma at days 0, 7, and 14.
3. To compare genetic differences between recipients of the anti-SARS-CoV-2 plasma and control plasma to explore possible associations with poor outcome.
4. To compare transcriptomic differences between recipients of the anti-SARS-CoV-2 plasma and control plasma at Day 0, 7, and 14 to explore possible associations with poor outcome.

Definitions

Enrolled: From time consented to participate until designated as a screen failure or have either been discontinued from the study or completed it. II. Randomized: when a study arm is assigned. III. Screen Failures: signed informed consent, but then determined to be ineligible or withdraws before being randomized. IV. Discontinued: randomized, but then withdrawn by investigator or withdraws consent. V. Completed: Subjects are considered completed when they are followed through to day 28, if they die before day 28, or are discharged prior to day 14.

Study population

Inclusion Criteria for Enrollment 1. Willing and able to provide written informed consent prior to performing study procedures or having a legally authorized representative available to do so. 2. Age ≥ 18 years. 3. Evidence of SARS-CoV-2 infection by PCR test of nasopharyngeal swab or oropharyngeal swab/tracheal aspirate sample within 14 days of randomization 4. $\text{SpO}_2 \leq 94\%$ on room air or requiring supplemental oxygen, non-invasive or invasive mechanical ventilation at screening 5. Evidence of infiltrates on chest radiography 6. Females of childbearing age and males must be willing to practice an effective contraceptive method or remain abstinent during the study period.

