- Most reactions to plasma are relatively minor and the infusion can generally be continued. Infusion site burning and non-allergic systemic effects can generally be managed with slowing of the infusion. Infusion is generally stopped in cases of itching; participant is treated and then infusion cautiously re-started.
- Severe allergic reactions generally require discontinuation of the infusion. These include:

 - Respiratory compromise: dyspnea, wheezing, stridor, hypoxemia A decrease in systolic blood pressure to < 90 mmHg or $>30\%$ decrease from baseline or a diastolic drop of $>30\%$ from baseline.
 - Tachycardia with an increase in resting heart rate to > 130 bpm; or bradycardia.

Concomitant medications will be documented on the CRF:

- Prescription medications
- Over the counter medications
- Herbal treatments/nutritional supplements
- Blood products

Prohibited Medications:

Any approved or investigational drug* with established or potential activity against SARS-CoV-2 given within 24 hours of plasma infusion. *Concurrent use of Remdesivir as treatment for COVID-19 during the course of the study is permitted.

STATISTICAL CONSIDERATIONS AND DATA MANAGEMENT

Design Overview

This randomized blinded phase 2 trial will assess the efficacy and safety of anti-SARS-CoV-2 plasma among adults with severe COVID-19. Eligible participants will be randomized in a 2:1 ratio to receive anti-SARS-CoV-2 plasma or fresh frozen plasma without known anti-SARS-CoV-2 antibodies. We plan to enroll up to 220 participants (US and Brazil). Each participant will be evaluated at baseline and daily during the follow-up period using a seven-category severity scale: 1. Not hospitalized with resumption of normal activities, 2. Not hospitalized, but unable to resume normal activities, 3. Hospitalized, not requiring supplemental oxygen, 4. Hospitalized, requiring supplemental oxygen, 5. Hospitalized, requiring high-flow oxygen therapy or noninvasive mechanical ventilation, 6. Hospitalized, requiring extracorporeal membrane oxygenation (ECMO), invasive mechanical ventilation, or both, and 7. Death.

According to the inclusion/exclusion criteria, all enrolled participants will have a score ranging 3–6 on this scale at baseline. The primary study endpoint is defined as the Day 28 outcome on the scale.

Safety will also be evaluated daily. Secondary endpoints include:

- SARS-CoV-2 PCR positivity from nasopharyngeal swab, collected on baseline (Day 0), Days 7, and 14.

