- Levels of SARS-CoV-2 RNA on Days 0, 7, and 14.
- Duration of need for supplemental oxygen and/or mechanical ventilation
- Duration of hospitalization
- Mortality.

Statistical Analysis

• Efficacy Objective

1. Primary Analysis, go/no-go decision, and power consideration

The primary analysis of the endpoint will be a one-sided nonparametric stratified Mann-Whitney test; stratification is done by country (US, Brazil). A “go decision” in this phase 2 trial will be a one-sided $P < .015$, suggesting evidence of promise of the treatment arm for further investigation in a phase 3 trial. Adaptive seamless phase 2/3: The results in this proof-of-concept study will be used to plan the sample size in a Phase 3 trial, which may include the data in this Phase 2 in the final analysis using adjusted P value as in a seamless phase 2/3 trial. Details of P value adjustment and sample size calculation will be decided before the final analysis of this study data.

The calculation was based on blinded pooled data of the Day 28 outcome and an odds ratio of 1.7 under a proportional odds assumption. With a 2:1 randomization ratio and a total sample size of 219 participants (146 in convalescent plasma vs. 73 control), a onesided Mann Whitney test at 15% level will have about 82% power to detect an odds ratio of 1.7. Since the difference in power between 219 and 220 is minimal, $N=219$ can be used to justify an enrollment total of 220. We note a recent study of antiviral drug yields an odds ratio of 1.15, with 95% CI: 0.67 to 1.96, which covers our assumed odds ratio.

2. Secondary and Ancillary Analyses

All secondary and ancillary efficacy analyses will also be intent-to-treat. With a sample size of 220, assuming 20% mortality up to day 28, we expect a total of 43 events. Longitudinal data collected over multiple days during the study period (e.g., PCR positivity, RNA) will be analyzed using the framework of generalized linear mixed model. Time-to-event variables (e.g., time to death) will be analyzed using Cox proportional hazards model. Continuous variables (e.g. duration of hospitalization) will be analyzed using Mann Whitney test. Treatment effects on these variables will be estimated with 95% confidence intervals.

3. Safety Analyses

Serious adverse events will be summarized by grades and types using proportions and 95% confidence intervals for the two study arms. Relative safety profile of the two arms will be compared using Fisher's exact test.

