4. Missing data and non-compliance

We will compare the missing data patterns between the study arms; and perform sensitivity analyses using different imputation approaches. However, due to the short study period, we anticipate minimal missing data. All efficacy analyses will be done intent-to-treat, although as-treat analyses will also be conducted as sensitivity.

STUDY PROCEDURES

Screening

- A. Screening (must be completed before randomization)
- B. Informed consent (obtained before performing study related activities)
- C. Baseline Evaluation (at screening) 1. Demographics (age, sex, ethnicity, race) 2. Medical history (acute and chronic medical conditions, medications, allergies) (any medical condition arising after consent should be recorded as AE) 3. COVID-19 symptom screen (fever, cough, shortness of breath) 4. Confirmation of SARS-CoV-2 testing (RT-PCR) for eligibility (within 14 days of randomization) 5. Vital signs 6. Physical examination 7. Blood typing 8. Urine or serum pregnancy test for females of childbearing potential. Results from laboratory tests obtained up to 7 days before enrollment may be used for the pregnancy test. 9. Determination of eligibility as per inclusion/exclusion criteria

Baseline (Randomization)

- 1. Randomization of eligible subject 2. Vital signs 3. COVID-19 symptom screen (fevers, cough, shortness of breath) 4. New medical conditions, concomitant medication 5. Assessment of clinical status (using 7-point ordinal outcome scale) 6. CBC, comprehensive metabolic panel (abstracted from routine clinical lab results in electronic medical record) 7. Stored samples for future studies (only if feasible) 8. SARS-CoV-2 testing (RT-PCR) from nasopharyngeal swab (only if feasible)

Day 0 Infusion (Within 48 hours from randomization) 1. Study Plasma Administration: A single unit of plasma will be transfused. Time at start and end of infusion will be recorded and vital signs will be measured immediately prior to infusion, 10-20 minutes after start of infusion, and at completion of

infusion. 2. Vital signs 3. Physical examination (acceptable to use clinician notes from electronic medical record) 4. COVID-19 symptom screen (fevers, cough, shortness of breath) 5. New medical conditions, concomitant medication, AE evaluation

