Day 1 ± 1 1. Vital signs 2. COVID-19 symptom screen (fevers, cough, shortness of breath) 3. Assessment of clinical status (using 7-point ordinal outcome scale) 4. New medical conditions, AE evaluation 5. Physical examination (acceptable to use clinician notes from electronic medical record) 6. CBC, comprehensive metabolic panel (abstracted from routine clinical lab results in electronic medical record) 7. Stored samples for future studies (only if feasible)

Day 3 ± 2 1. Vital signs 2. COVID-19 symptom screen (fevers, cough, shortness of breath) 3. Assessment of clinical status (using 7-point ordinal outcome scale) 4. New medical conditions, AE evaluation 5. Physical examination (acceptable to use clinician notes from electronic medical record)

Day 7 ± 2 1. Vital signs 2. COVID-19 symptom screen (fevers, cough, shortness of breath) 3. Assessment of clinical status (using 7-point ordinal outcome scale) 4. New medical conditions, AE evaluation 5. Physical examination (acceptable to use clinician notes from electronic medical record) 6. SARS-CoV-2 testing (RT-PCR) from nasopharyngeal swab (only if feasible) 7. CBC, comprehensive metabolic panel (abstracted from routine clinical lab results in electronic medical record) 8. Stored samples for future studies (only if feasible)

Day 14 ± 2 1. Vital signs 2. COVID-19 symptom screen (fevers, cough, shortness of breath) 3. Assessment of clinical status (using 7-point ordinal outcome scale) 4. New medical conditions, AE evaluation 5. Physical examination (acceptable to use clinician notes from electronic medical record) 6. SARS-CoV-2 testing (RT-PCR) from nasopharyngeal swab (only if feasible) 7. CBC, comprehensive metabolic panel (abstracted from routine clinical lab results in electronic medical record) 8. Stored samples for future studies (only if feasible)

Day 28 ± 3 1. Vital signs 2. COVID-19 symptom screen (fevers, cough, shortness of breath) 3. Assessment of clinical status (using 7-point ordinal outcome scale) 4. New medical conditions, AE evaluation 5. Physical examination (acceptable to use clinician notes from electronic medical record)

EFFICACY, VIROLOGIC AND PK MEASURES

Primary Endpoint:

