Day 28 severity outcome on a seven-category ordinal scale consisting of the following categories: 1. Not hospitalized with resumption of normal activities 2. Not hospitalized, but unable to resume normal activities 3. Hospitalized, not requiring supplemental oxygen 4. Hospitalized, requiring supplemental oxygen 5. Hospitalized, requiring high-flow oxygen therapy or noninvasive mechanical ventilation 6. Hospitalized, requiring extracorporeal membrane oxygenation (ECMO), invasive mechanical ventilation, or both 7. Death

Virologic measures:

1. Rates and duration of SARS-CoV-2 PCR positivity (RT PCR) at days 0, 7 and 14.
2. Peak quantity levels of SARS-CoV-2 RNA at days 0, 7 and 14.

RISKS AND BENEFITS

Potential benefits of treatment

The potential benefits of antiviral treatment with anti-SARS CoV-2 plasma in patients with severe COVID-19 is unknown. However, based on available evidence from use of convalescent plasma in SARS-CoV-1 patients, shortened duration of illness and improved mortality are potential benefits.

Potential benefits of clinical monitoring and virologic testing

Subjects enrolled in the study will undergo close virological monitoring that may facilitate improved understanding of viral shedding that may have benefit to the individual, their family and the community at large.

Potential risks of study procedures

1. Risks of plasma: Fever, chills, rash, headache, serious allergic reactions, transmission of infectious agents
2. Transfusion related acute lung injury (TRALI) and transfusion related circulatory overload (TACO), both of which may worsen oxygen saturation and increase work-of-breathing
3. Risks of phlebotomy: local discomfort, bruising, hematoma, bleeding, fainting
4. Total blood draws will not exceed 500 mL
5. Risks of nasopharyngeal swab: local discomfort, vomiting
6. Risks of IV placement: bleeding, infection, thrombosis

Potential risks of genetic testing

Samples obtained for future research may include a search for genetic correlates of COVID-19 susceptibility or severity. Specimens will be labeled by study IDs, rather than names. This information will not be released to participants and will not become part of their medical records. Risks related to discrimination or other problems are deemed highly unlikely.

Alternatives

The alternative to participation in this study is continued standard-of-care clinical management.

Safety monitoring

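### Three optional swabs give interval-censored PCR clearance, not a duration, and counting patients already negative at Day 0 dilutes the comparison of arms

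*Combined protocol and SAP*

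**What the plan says.** The Ancillary Endpoints in the synopsis and in Study Objectives both compare the proportion and the duration of PCR positivity between arms. Virologic measures item 1 repeats this as "Rates and duration of SARS-CoV-2 PCR positivity (RT PCR) at days 0, 7 and 14".

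The Design Overview gives the sampling as "SARS-CoV-2 PCR positivity from nasopharyngeal swab, collected on baseline (Day 0), Days 7, and 14". In Study Procedures the baseline, Day 7 ± 2 and Day 14 ± 2 visits each list "SARS-CoV-2 testing (RT-PCR) from nasopharyngeal swab (only if feasible". The Day 28 visit lists no swab. The baseline swab appears under Baseline (Randomization), after the step that randomizes the patient, and infusion may follow up to 48 hours after randomization.

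Inclusion criterion 3 asks for "Evidence of SARS-CoV-2 infection by PCR test of nasopharyngeal swab or oropharyngeal swab/tracheal aspirate sample within 14 days of randomization". The qualifying test can therefore be two weeks old and from a different site than the endpoint swab.

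Secondary and Ancillary Analyses makes these analyses intent-to-treat. It sends repeated PCR results and RNA to a generalized linear mixed model, time-to-event variables to a Cox model, and states: "Continuous variables (e.g. duration of hospitalization) will be analyzed using Mann Whitney test". It does not say which method applies to the duration of PCR positivity. No section defines when positivity starts or ends, how to treat a patient still positive at the last swab, or what a Day 0 negative contributes.

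**The concern.** A duration in days is promised, but the samples place clearance only in broad intervals. Without a derivation rule, the scoring and the denominator can be chosen after the data are seen.

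The denominator matters more than the scoring. A patient negative on the Day 0 swab cannot clear any faster under treatment, so including such patients pulls the arms together and adds chance imbalance. The Background names viral neutralization as the anticipated mechanism, and viral clearance is the nearest measure of it in this trial. A null result caused by the denominator could be misread as evidence against antiviral activity.

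**Working it through.** The plan states no clearance rate, effect size or power for this measure, so there is no figure of its own to reproduce. The check runs in five steps.

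**1. What the swabs can show.** A patient with all three swabs falls into one of four groups: negative at Day 0, cleared between the first and second swab, cleared between the second and third, or still positive at the third. The windows are Days 5–9 and 12–16. The first gap is 5 to 9 days from Day 0, or up to 9 + 2 = 11 if the baseline swab precedes infusion by 48 hours. The second gap runs from 12 − 9 = 3 to 16 − 5 = 11 days. Clearance on Day 1 and on Day 6 can look the same. The data are interval-censored, and right-censored at the last swab.

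**2. Inputs for size.**
- From the documents: 220 patients randomized 2:1 (about 147 and 73), swabs at nominal Days 0, 7 and 14, and 95% confidence intervals (hence two-sided 5%).
- Assumed: exponential clearance with control median 10 days, hazard ratio 1.5, a share f already negative at Day 0 of 0, 20% or 40%, no missing swabs and no deaths.

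**3. Expected difference.** The proportion still positive is S(t) = 2^(−HR·t/10).
- Control: S(7) = 0.616, S(14) = 0.379.
- Treated: S(7) = 0.483, S(14) = 0.233.
- Score clearance at the interval midpoint (3.5 or 10.5 days), or 14 if still positive. Control mean: 3.5 × 0.384 + 10.5 × 0.237 + 14 × 0.379 = 9.14. Treated mean: 3.5 × 0.517 + 10.5 × 0.250 + 14 × 0.233 = 7.70. The difference is 1.44 days.
- With Day 0 negatives scored 0, this becomes (1 − f) × 1.44, which is 1.15 days at 20% and about 0.87 at 40%.
- A rank test is hit harder. Pairs with one Day 0 negative cancel on average, and only pairs with both patients positive carry the effect. The rank contrast therefore falls by (1 − f)², to 0.64 and 0.36 of its size.

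**4. Simulated power.** Repeat runs differ by one to three points.

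| Share negative at Day 0 | Mann-Whitney on duration: everyone | Mann-Whitney: Day 0 positives | Repeated positivity model: everyone | Repeated model: Day 0 positives |
|---|---|---|---|---|
| 0% | 62% | 62% | 65% | 65% |
| 20% | 30% | 53% | 50% | 57% |
| 40% | 13% | 43% | 36% | 46% |

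The repeated model is a logistic model of positivity at Days 7 and 14, fitted by generalized estimating equations as a stand-in for the planned mixed model. An interval-censored model in Day 0 positives estimates the hazard ratio at 1.51, 1.52 and 1.53 (true value 1.5), with power 65%, 55% and 43%.

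**5. Coarse spacing on its own.** With no Day 0 negatives, Mann-Whitney power on exact times capped at Day 14 is 61%, against 62% on the swab grid. Spacing costs almost nothing here.

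A second set of assumptions (Weibull, shape 1.5, swabs uniform over the windows) separates spacing from the end of follow-up:

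| True medians, days | Mean difference, unlimited follow-up | Exact times capped at Day 14 | Last positive day (0, 7, 14) |
|---|---|---|---|
| 10 vs 8 | 2.3 | 1.15 | 1.50 |
| 14 vs 11 | 3.5 | 1.03 | 1.47 |
| 20 vs 15 | 5.8 | 0.90 | 1.36 |

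The loss from the second column arises because follow-up stops at Day 14. Last-positive-day scoring does not shrink the difference below what exact times to Day 14 would show.

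**The case against.** The strongest reply is that the plan already has a sound virology analysis. Repeated PCR positivity goes to a mixed model that needs no duration. The Mann-Whitney example concerns hospital stay, and nothing says that the last positive day will be the score. All of this stands. The larger power losses above apply only if a duration is formed and compared by ranks, which is an inference from silence.

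A reader might infer that coarse swabs bias the treatment difference toward zero, or that a real difference disappears. Step 5 does not support the first. On the second, the expected difference shrinks by the Day 0 negative share but stays above zero in every scenario examined; what can collapse is power. A reader might also infer that no clearance analysis is possible. That holds only for an exact duration, since the same swabs return the hazard ratio almost without bias.

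It is also fair to object that a Day 0 positive set is not automatically protected by randomization. The baseline swab is optional and listed after randomization, and under Intervention the clinical study team is not blinded. Whether a swab is taken could depend on the arm. This stands, and the fix needs a check for it.

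Finally, the share of Day 0 negatives is not in the documents, so every figure for dilution is conditional on it.

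**Conclusion.** The concern holds in limited form. The duration of PCR positivity cannot be observed as an exact number of days, and it has no derivation rule. Under intent-to-treat with no restriction, patients already negative at Day 0 are included and dilute the comparison. Under the stated assumptions the mean difference falls in proportion to their share. At 20% negative, Mann-Whitney power on duration is about 30% rather than 53%; the planned type of model for positivity gives about 50% rather than 57%. These figures ignore missing swabs, deaths and early discharge, none of which has a rule for this measure. The Definitions count discharge before Day 14 as completion, so the last swab may be absent in such patients.

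The Study Objectives class the measure as ancillary. The go decision uses only the Day 28 scale, so nothing here bears on it. This is a cheap improvement, not a flaw in the primary analysis.

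**What to change.** In both Ancillary Endpoints lists and in Virologic measures, replace duration with time to first negative nasopharyngeal PCR. In Secondary and Ancillary Analyses, state that:

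- It is analysed as interval-censored between actual swab dates and right-censored at the last positive swab, with explicit rules for missed swabs, death and early discharge.
- Patients positive on the pre-infusion swab form the main set for this measure and for positivity at Days 7 and 14. All randomized patients are reported as supportive.
- The availability of a baseline swab is compared between arms, because that swab is optional and listed after randomization.

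This changes wording only and uses swabs and dates already scheduled. The price is that patients with a negative or missing baseline swab leave the main virology set. It does not recover what happens after Day 14, because re-analysis cannot replace later swabs.

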NCT04359810

Protocol (Population A) V 17AUG2020

Long title: A Phase 2, Randomized Clinical Trial to Evaluate the Efficacy and Safety of Human Anti-SARS-CoV-2 Convalescent Plasma in Severely Ill Adults with COVID-19 (AAAS9924)

Short title: Population A: Convalescent Plasma in Severe COVID-19 Clinical

Phase: 2 IND Sponsor: [name]

Principal Investigator: [name], MPH

Conducted by: Columbia University

Sample Size: 220

Study Population: Subjects aged ≥ 18 years with severe COVID-19

Study Duration: Approximately 1 year.

Study Design: Randomized blinded phase 2 trial to assess the efficacy and safety of anti-SARS-CoV-2 plasma among adults with severe COVID-19. A total of 220 eligible subjects will be randomized in a 2:1 ratio, stratified by country (US, Brazil) to receive either convalescent plasma qualitatively positive for SARS-CoV-2 antibody (anti-SARS-CoV-2 plasma) or non-convalescent fresh frozen plasma (control plasma). The patient and the study clinician assessing the clinical outcome will be blinded to the treatment arm.

The following will be assessed in all subjects:

Safety and efficacy: Day 0 (baseline) to Day 28.

Study Agent:

- Anti-SARS-CoV-2 convalescent plasma (1 unit; ~200-250 mL collected by apheresis from a volunteer who recovered from COVID-19 (collection and qualification covered by IRB protocol AAAS9845 (Convalescent plasma donors)) and was found to be a qualitatively positive for SARS-CoV-2 antibody ("anti-SARS-CoV-2 plasma").
- Control plasma: 1 unit of standard plasma collected prior to December 2019 Protocol (Population A) V 17AUG2020

Primary Efficacy Objective: To evaluate the efficacy of treatment with anti-SARS-CoV-2 plasma versus control plasma with respect to Day 28 severity outcome.

Primary Endpoint: The primary endpoint is Day 28 severity outcome on a seven-category scale:

1. Not hospitalized with resumption of normal activities
2. Not hospitalized, but unable to resume normal activities
3. Hospitalized, not requiring supplemental oxygen
4. Hospitalized, requiring supplemental oxygen
5. Hospitalized, requiring high-flow oxygen therapy or noninvasive mechanical ventilation
6. Hospitalized, requiring extracorporeal membrane oxygenation (ECMO), invasive mechanical ventilation, or both
7. Death

Primary Safety Objective: To evaluate the safety and tolerability of treatment with anti- SARS-CoV-2 plasma versus control (control plasma) in adults with severe COVID-19.

Primary Safety Endpoints:

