1. Cumulative incidence of grade 3 and 4 adverse events during the study period
2. Cumulative incidence of serious adverse events during the study period

Secondary Objectives:

1. To compare duration of need for supplemental oxygen and/or mechanical ventilation between recipients of the anti-SARS-CoV-2 plasma and control plasma.
2. To compare duration of hospitalization between recipients of the anti-SARSCoV-2 plasma and control plasma.
3. To compare in-hospital and 28-day mortality between recipients of the anti-SARS-CoV-2 plasma and control plasma.

Ancillary Endpoints:

1. To compare the proportion and duration of SARS-CoV-2 PCR positivity (RT PCR) between the recipients of the anti-SARS-CoV-2 plasma and control plasma at days 0, 7, and 14.
2. To compare the levels of SARS-CoV-2 RNA between recipients of the anti-SARS-CoV-2 plasma and control plasma at days 0, 7, and 14.
3. To assess for genetic and transcriptomic differences at Day 0 (genomic) and Day 0,7,14 (transcriptomic) between the recipients of the anti-SARS-CoV-2 plasma and control plasma.

STUDY POPULATION

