1. Safety Evaluations: Will assess for the safety of anti-SARS-CoV-2 plasma in terms of treatment emergent adverse events.
2. Clinical evaluations: Vital signs and symptom screen on days 0-28 (or until hospital discharge, whichever is sooner).
3. Laboratory evaluations:
4. Safety laboratory tests (ABO typing, pregnancy testing, CBC and comprehensive metabolic panel) will be performed at the local CLIA-certified hospital clinical laboratory on days 0-14 (or until hospital discharge, whichever is sooner).

Adverse event reporting

An Adverse Event (AE) is any untoward or unfavorable medical occurrence in a human subject administered an investigational product, including any abnormal sign, symptom or disease, temporally associated with the subject's participation in research, whether or not considered related to the subject's participation in the research.

An AE does not include the following:

- Medical or surgical procedures such as surgery, endoscopy, tooth extraction, and transfusion. The condition that led to the procedure may be an AE and must be reported.
- Preexisting diseases, conditions, or laboratory abnormalities present or detected before the screening visit that do not worsen
- Situations where an untoward medical occurrence has not occurred (e.g., hospitalization for elective surgery, social and/or convenience admissions)
- Any medical condition or clinically significant laboratory abnormality with an onset date before the investigational product is administered to the subject and not related to a protocol-associated procedure is not an AE. It is considered to be preexisting and should be documented as medical history.

Preexisting events or conditions that increase in severity or change in nature after the subject receives the investigational product will be considered AEs.

Serious Adverse Event (SAE): any adverse event temporarily associated with the subject's participation in research that meets any of the following criteria:

- Results in death;
- Is life-threatening (places the subject at immediate risk of death from the event as it occurred);
- Requires inpatient hospitalization or prolongation of existing hospitalization;
- Results in a persistent or significant disability/incapacity;
- Results in a congenital anomaly/birth defect; or

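### The protocol conflicts with itself on whether symptom screening and follow-up continue after discharge, so non-fatal events after discharge may be under-captured in primary safety endpoints that run to Day 28

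*Combined protocol and SAP*

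**What the plan says.** Two passages point to follow-up ending at discharge.

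- Safety monitoring, item 2: "Vital signs and symptom screen on days 0-28 (or until hospital discharge, whichever is sooner". Item 4 limits safety laboratory tests in the same way, "on days 0-14 (or until hospital discharge, whichever is sooner".
- Definitions, item V, counts a subject as completed when followed to Day 28, when dead before Day 28, or when discharged before Day 14.

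Three point to follow-up of everyone to Day 28.

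- Synopsis, for all subjects: "Safety and efficacy: Day 0 (baseline) to Day 28".
- Study Procedures, last visit: "Day 28 ± 3 1. Vital signs 2. COVID-19 symptom screen (fevers, cough, shortness of breath". The entry "New medical conditions, AE evaluation" appears at Days 1, 3, 7, 14 and 28, with no discharge condition.
- Design Overview: "Safety will also be evaluated daily".

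The first primary safety endpoint is "Cumulative incidence of grade 3 and 4 adverse events during the study period"; the second is the same quantity for SAEs. The Safety Analyses section says "Serious adverse events will be summarized by grades and types using proportions and 95% confidence intervals for the two study arms", with Fisher's exact test between arms. It gives no person-time, censoring or observed-time rule. The missing-data section expects little missingness and does not mention safety data after discharge.

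**The concern.** A cumulative incidence to Day 28, analysed as a plain proportion, is sound only if every subject is observed to Day 28 with similar completeness. A site that works from Safety monitoring item 2 and the completion definition could stop active follow-up at discharge. A subject with no later contact would then contribute no events, and nothing in the analysis section separates that subject from one who was asked and had none.

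This matters more than ordinary missingness because duration of hospitalization is a secondary objective and discharge defines scores 1 and 2 of the primary scale. If the treatment works, time in hospital differs by arm, and so does the time under close observation. The background section names acute renal failure and thromboembolic events as late, though rare, adverse events, so the period after discharge is not irrelevant to safety.

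**Working it through.** The plan states no figure for AE rates, length of stay or post-discharge capture, so there is nothing to reproduce. The arm sizes (146 and 73) come from the power paragraph. **Every other input below is an assumption.**

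**Model 1: variable stays.** Inpatient time T follows a gamma distribution with shape 1.5, cut at 28 days. The event hazard is h per day in hospital and k·h after discharge, the same in both arms. A fraction c of post-discharge events is captured. The observed proportion is

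1 − E[exp(−h·T − h·k·c·(28 − T))].

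Untruncated mean stays of 12 vs 15 days (convalescent plasma vs control) give 11.4 vs 13.5 inpatient days within 28, that is 41% vs 48% of the period. Means of 10 vs 14 give 9.7 vs 12.8.

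With k = 1, the true 28-day incidence in each arm is 1 − exp(−0.015 × 28) = 0.343 or 1 − exp(−0.03 × 28) = 0.568:

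| Mean stays | h per day | Captured (c) | Convalescent plasma | Control | Risk ratio |
|---|---|---|---|---|---|
| 12 vs 15 | 0.015 | none | 0.1508 | 0.1765 | 0.854 |
| 12 vs 15 | 0.015 | half | 0.2543 | 0.2660 | 0.956 |
| 12 vs 15 | 0.03 | none | 0.2693 | 0.3109 | 0.866 |
| 12 vs 15 | 0.03 | half | 0.4420 | 0.4589 | 0.963 |
| 10 vs 14 | 0.015 | none | 0.1307 | 0.1685 | 0.776 |
| 10 vs 14 | 0.015 | half | 0.2453 | 0.2623 | 0.935 |
| 10 vs 14 | 0.03 | none | 0.2363 | 0.2980 | 0.793 |
| 10 vs 14 | 0.03 | half | 0.4288 | 0.4537 | 0.945 |

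With full capture the ratio is 1.000 in every row.

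If the hazard falls after discharge, the ratio is compared with its own full-capture value. With no capture, the bias is 10% to 17% at k = 0.5 and 7% to 12% at k = 0.25. With half capture, across k = 1, 0.5 and 0.25, it is about 3% to 7%, and each arm is under-counted by about 10% to 28%.

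**Model 2: fixed discharge days.** As a check by a simpler route, take a true 28-day incidence P in both arms, λ = −ln(1 − P)/28, discharge on day d and captured fraction φ. The observed proportion is 1 − exp(−λ·(d + φ·(28 − d))). For P = 30%, λ = 0.01274. With discharge on Day 10 vs Day 14, and two-sided 5% Fisher rejection enumerated exactly at 146 vs 73:

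| Captured (φ) | Convalescent plasma | Control | Ratio | Fisher rejection |
|---|---|---|---|---|
| 0 | 12.0% | 16.3% | 0.73 | 12.9% |
| 0.5 | 21.5% | 23.5% | 0.92 | 5.4% |
| 0.9 | 28.4% | 28.7% | 0.99 | 4.2% |
| 1 | 30.0% | 30.0% | 1.00 | 4.2% |

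For Day 7 vs Day 14 the ratios at φ = 0, 0.5 and 0.9 are 0.52, 0.85 and 0.98. Over true incidences of 20% to 50% and both discharge scenarios, the ratio runs from 0.51 to 0.75 with no capture, 0.84 to 0.93 with half, and 0.98 to 0.99 at 90%.

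The direction is the same in both models. The size depends on how much is captured after discharge, which is what the protocol leaves undefined.

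**The case against.** A reader might infer that AE collection stops at discharge, that all later time is scored as event-free over the whole arm, and that the convalescent plasma arm will therefore look safer. The documents do not support that reading.

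- Item 2 limits only vital signs and a symptom screen covering fever, cough and shortness of breath. AE evaluation is a separate line in Study Procedures, and the reporting rules require all AEs and SAEs to be reported on awareness, with no discharge cut-off.
- A Day 28 contact is needed anyway, because scores 1 and 2 separate discharged patients by whether they have resumed normal activities.
- Deaths and subjects in hospital at Day 28 are seen through the primary scale and 28-day mortality.
- The Safety Analyses name proportions for SAEs only and do not define the denominator. The whole arm is a fair inference, not written text.
- The tilt between arms needs both unequal discharge times and incomplete capture.
- The zero-capture figures set aside the scheduled AE evaluations and, in the table, assume that risk does not fall after discharge. The treatment is one infusion. If the hazard instead decays with a mean of 5 days and the total stays at 34.3%, Model 1 gives ratios of 0.92 to 0.95 with no capture and 0.97 to 0.98 with half.

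All of this stands, and it limits the size of the problem. It does not remove the conflict. The protocol does not say how AEs are collected from discharged subjects, and the completion definition allows a subject to be closed before the Day 28 evaluation.

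**Conclusion.** The point holds as a conflict within the protocol that bears on the primary safety endpoints. It is not evidence that the safety comparison will be biased. Safety monitoring item 2 and the completion definition cannot both be followed alongside Day 0 to Day 28 safety assessment of all subjects and the unconditional Day 14 and Day 28 evaluations.

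If the discharge cut-offs prevail, the loss falls mainly on non-fatal grade 3-4 AEs and resolved SAEs after discharge. Both arms are under-counted whether or not discharge times differ; the between-arm tilt arises only if they do. Half capture is the more plausible of the two cases in the Model 1 table, given the scheduled evaluations, and the bias is then a few percent. The zero-capture range is an outer case. At 90% capture the effect is negligible (ratio 0.98 to 0.99 in Model 2). The change is worth making because it is cheap and settles the question. The power calculation for the primary efficacy endpoint is unaffected.

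**What to change.** 1. Reword Safety monitoring item 2 so that vital signs and symptom screens run while the subject is in hospital, and discharged subjects receive the symptom screen and AE evaluation at the Day 14 and Day 28 contacts in Study Procedures. The AE evaluation should ask about grade 3-4 AEs and SAEs since the last contact. Deleting the discharge clause alone is not enough, because it would leave screening on days 0-28 for outpatients.
2. Make the Day 14 and Day 28 entries in Study Procedures agree with this.
3. Amend Definitions item V so that discharge before Day 14 does not end follow-up for safety or for the Day 28 outcome.
4. Report by arm the number of subjects with AE evaluation completed to Day 28.

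A table of AEs per inpatient day is not recommended. It conditions on a post-randomization outcome: under the decaying hazard above, with no true difference and no post-discharge capture, the AE proportion divided by mean inpatient days is 0.0238 vs 0.0211 (ratio 1.13), or a ratio of 1.21 with the shorter stays. That would count against the arm discharged sooner.

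The cost is protocol wording, a few questions at contacts already scheduled, one line in a safety table, and slightly higher AE counts.
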